3. SUBJECTS

a. Description of Study Populations

- Participants will be 18 to 50 years old and will be diagnosed with one of the following: generalized anxiety disorder, panic disorder, SAD, specific phobias, major depression, and bipolar depression according to DSM-IV. Patients on scheduled/regular psychotropic medications, other than lithium or Depakote, will stay on their medication. Although patients will not be taken off medications for the purposes of this study, included patients will not be currently taking psychiatric medications or any other medications that may interfere with study results (see exclusion criteria for other characteristics of patient sample). The only

exception is that bipolar depressed patients may be taking mood stabilizers, either lithium carbonate or Depakote. Subjects taking PRN medication that is allowed according to the medication table below, must be both willing and safely able to hold the medication for 5 half-lives. Additionally, healthy controls who are age and sex matched to patients will be studied.

- The accrual ceiling is 608 patients with mood or anxiety disorders and 663 healthy volunteers. This accrual ceiling includes a drop out/withdrawal/non-analyzable data rate of 15% for sub-studies 1 (11 patients, 44 controls) and 2 (115 patients, 86 controls) and 25% for sub-study 3 (38 patients, 38 controls).
- NIH, but not NIMH, employees may participate. NIH employee participation is guided by intramural institute policy.

b. Inclusion criteria for both patients and healthy controls

- All subjects must be able to give written informed consent prior to participation in this study.
- PATIENTS ONLY: May have DSM-IV-TR diagnoses of an anxiety disorder (GAD; SAD; Panic disorder; specific phobia) or mood disorder (MDD; BP).
- PATIENTS ONLY: May be taking the mood stabilizers, Depakote or Lithium Carbonate.
- Speaks English fluently
-

c. Exclusion criteria for healthy subjects

- Female subjects who are currently pregnant
- Subjects who meet DSM-IV criteria for current alcohol or substance abuse
- Subjects with a history of alcohol or substance dependence within 6 months prior to screening
- Current Axis I psychiatric disorders as identified with the Structured Clinical Interview for DSM-IV-TR axis disorders, non-patient edition (SCID-np). Past history of any psychotic disorder or bipolar disorder.
- IQ < 80

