
- Healthy volunteers may also be identified or screened through the NIMH protocol #17-M-0181 titled "Recruitment and Characterization of Research Volunteers for NIMH Intramural Studies."
- Audio advertisements will be played during radio or podcasts, Potential radio stations may be public radio (i.e., WAMU) or other mainstream radio stations (i.e., 97.1 Fresh FM). Potential podcasts may be ones like Ted Radio Hour, Moth, Criminal, Diane Rehm, etc.
- An animated short video advertisement may also be posted on the NIMH YouTube channel. This video may be posted on official NIH, NIMH, and NIH Clinical Center social media accounts such as Facebook, Instagram, and Twitter. It may be sent via electronic

listservs such as NIH postbac listserv, community listservs, advocacy and provider listservs, and running/ health listservs.

- We may use paid advertising on social media sites, such as Facebook, Instagram, and Twitter, to recruit potential volunteers whom are within our age range and located near the NIH (within 50 miles). We will not use behavioral targeting for any advertising campaign. We will target all potential volunteers within that age range (18-50 years old) and location (within 50 miles) and will not specifically target anxiety volunteers. We will only use advertisements and videos that have been previously IRB approved. Accounts used for Twitter, Facebook, and Instagram are the NIH sponsored accounts.
- Potential subjects will undergo an initial pre-screening by phone. (See Appendix A) This is done prior to consent procedures to determine potential eligibility. During the phone screen, the following will be described: a) purpose and goals of the study, b) the experimental procedures involved, c) the time commitment required, d) compensation, and e) inclusion/exclusion criteria. It will be emphasized to participants that unpleasant shocks and air puffs will be administered during the course of the study. If individuals are interested in participating in the study they will be given an appointment to come to NIH for a first visit. In addition to receiving information via telephone, potential participants will receive complete information about this study by mail including actual copies of the consent form.
- Mood Disorder Patients will be referred by [name]'s group (NIMH/). We will be recruiting patients from [name] group, who already have been cleared under the screening protocol (01-M-0254).

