• Mood and anxiety disorders are associated with deficits in attention control. As an exploratory aim, we will examine whether measures of memory and sustained attention relate to any experimental measures. English-speaking participants will be tested on the following cognitive tests:

- Digit Span: In this test of memory capacity, subjects are presented with a series of digits (e.g., 2, 4, 9, 7) and must repeat them back;
- Corsi test: In this visuo-spatial short-term memory test, subjects are shown 9 blocks on a monitor. The subjects observe a sequence of blocks that lit up. Their task is to repeat the sequence. The task begins with a small number of blocks and then gradually involves more blocks;
- Go-NoGo Task; in this test of sustained attention and impulsivity, subjects are shown different letters one at a time. They have to press a button to each letter except infrequent x.

- Some participants may have participated in the NIMH healthy volunteer protocol #17-M-0181. For those participants, identifiable data may be shared between protocols 17-M-0181, 01-M-0254 and this protocol 03-M-0093. The information from 17-M-0181 may be used for screening for this protocol as long as: it has been within a year for the demographic information, medical history and physical examination, SCID, WASI, and questionnaires. The urine pregnancy and drug screen will need to be within two weeks. The urine pregnancy is also repeated prior to any study procedures on the study visit day under this protocol.
- Additional laboratory examinations (i.e. blood testing or EKG) may be completed if clinically indicated and if consent is obtained for those procedures.
- If the screening protocol (01-M-0254) finds them to be eligible, they will undergo the informed consent process for 03-M-0093.
- Following informed consent of the 03-M-0093 protocol, participants will complete the studies described below. Female participants will first have a urine pregnancy test. At the completion of each visit, patients will be clinically assessed for adverse reactions to experimental procedures and psychiatric intervention will follow when clinically indicated.

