9. OUTCOME MEASURES

- a. Primary outcome measures: Primarily, we are interested in exploring the affective, cognitive and behavioral of our study's dependent measures. The primary outcome measures will be the startle reflex and performance on cognitive tasks.
- b. Secondary outcome measures: These measures include psychophysiological measures other than startle (e.g., skin conductance) and state and trait questionnaires.

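### Healthy volunteers can be cleared on a SCID up to a year old, although the exclusions concern current status and the last 6 months, and no interval update is required

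*Combined protocol and SAP*

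**What the plan says.** Section 4.b (Recruitment) opens the route: "Healthy volunteers may also be identified or screened through the NIMH protocol #17-M-0181". Section 4.c then allows information from that protocol to be used for screening here, on one condition: "it has been within a year for the demographic information, medical history and physical examination, SCID, WASI, and questionnaires". Only the urine tests have a shorter limit: "The urine pregnancy and drug screen will need to be within two weeks".

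Section 3.c lists the exclusions for healthy subjects. Three depend on recent psychiatric or substance status:

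- on psychiatric disorder: "Current Axis I psychiatric disorders as identified with the Structured Clinical Interview for DSM-IV-TR axis disorders" (in the version for non-patients);
- on abuse: "Subjects who meet DSM-IV criteria for current alcohol or substance abuse";
- on dependence, with its look-back: "Subjects with a history of alcohol or substance dependence within 6 months prior to screening".

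On questionnaires, the Assessments text in section 4.d uses trait STAI to classify controls as high or low in trait anxiety, repeats state STAI before each task, and calls the remaining scales exploratory. Section 9 defines the secondary outcomes as "psychophysiological measures other than startle (e.g., skin conductance) and state and trait questionnaires". The primary outcomes there are startle and cognitive task performance.

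**The concern.** The exclusions ask about the person's condition now and over the last half year. The reuse rule allows that question to be answered with an interview from up to a year ago. The protocol sees that some screening data age quickly, since it limits the urine tests to two weeks and repeats the pregnancy test on the study day. It sets no comparable rule for psychiatric or alcohol status.

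What is at stake is the control group. A volunteer who developed an anxiety, mood or substance-use disorder after the 17-M-0181 interview could be counted as healthy. The patient-control contrasts in section 10 would then compare patients with a partly mislabelled group. A lesser issue is that trait and symptom scores imported for these controls could predate their startle session by many months.

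**Working it through.** **Inputs**

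- Maximum age of an imported SCID: 12 months (section 4.c).
- Look-back for dependence: 6 months before screening (section 3.c).
- Maximum age of the urine drug screen: two weeks (section 4.c). Alcohol is not among the substances listed.
- Planned controls in sub-study 1: 44 (section 10).

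The plan gives no figure for reused screening data, so there is none to reproduce.

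**Step 1: window against look-back.** The permitted age is 12/6 = 2 times the look-back. For a SCID that is *a* months old at screening for this study, the share of the look-back it cannot cover is min(*a*, 6)/6.

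| SCID age (months) | Share of look-back not covered |
|---|---|
| 0 | 0% |
| 0.5 | 0.5/6 = 8% |
| 3 | 3/6 = 50% |
| 6, 9 or 12 | 6/6 = 100% |

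If ages were spread evenly from 0 to 12 months (an assumption), the first half would average 50% and the second half 100%, so the mean is (50% + 100%)/2 = 75%.

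This takes the reference date to be screening for this study. The text does not say so. If it means the 17-M-0181 date, the interview covers the look-back, but the look-back can then end up to 12 months before screening for this study.

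**Step 2: current status.** Absence of a current disorder or current abuse has no look-back at all. An older interview of any age leaves the time since then unobserved, so 6 months is not a natural dividing line.

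**Step 3: do the other checks fill the gap?**

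| Check | Section | What it renews, as written |
|---|---|---|
| Phone pre-screen | 4.b | Describes the study and criteria; no diagnostic interview is described |
| In-person screening under 01-M-0254 | 4.a, 4.c | Has an eligibility check and a medication history, but the SCID is the only structured psychiatric interview listed for controls, and it may be the imported one |
| Urine drug screen | 4.c | Recent use of listed drugs; not alcohol, and not a diagnosis |
| Medication review before the visit | 4.d | Medication only |

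Each narrows the gap. None is stated to update psychiatric or alcohol status.

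**Step 4: how many controls?** The documents give neither the share using this route nor the incidence of new excluding conditions. Purely as an illustration, assume an annual incidence *i* of 1% to 10% and that every control uses the route.

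- All SCIDs 12 months old: share affected = *i*, or 1% to 10%. Of 44 controls, 44 × 0.01 = 0.4 to 44 × 0.10 = 4.4.
- Ages spread evenly: share affected = 1 − *i*/*r*, with *r* = −ln(1 − *i*). At 10%, *r* = 0.1054 and the share is 5.1%; at 1% it is 0.5%. Of 44 controls, 0.2 to 2.2.

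If only a fraction of controls uses the route, these counts shrink in proportion. They also give no credit to the checks in step 3.

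**Step 5: questionnaires.** State STAI and the primary outcomes are obtained at the visit, so they are current. Trait STAI and the other symptom scales have no stated repeat, so a reused volunteer's scores may be up to 12 months old.

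**The case against.** The strongest reply is that the route is narrow and guarded. Reuse is optional and applies to some healthy volunteers only. Every subject is still screened in person under 01-M-0254, which decides eligibility. The eligibility check and the medication history are not on the list of items that may be a year old. A clinician at that visit may well ask about the interval, and the documents that would show this (01-M-0254, 17-M-0181 and the phone-screen appendix) are not available here. Reuse is also granted for screening; nothing says that imported scores become analysis data.

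Much of this stands. It limits how many controls can be affected, and it means that outdated control scores are a possibility, not a fact. It does not remove the conflict. An eligibility check with no new psychiatric input can only apply the old interview, and this protocol requires no interval history. Nor does it say that questionnaires will be collected again, although trait questionnaires are a secondary outcome.

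**Conclusion.** The gap is real but minor. As written, the reuse rule can admit a control who fails an exclusion criterion. The size is unknown: the counts in step 4 rest entirely on assumed incidence and on every control using the route. For trait STAI and the exploratory scales, the point is that scores may be old for a subset of controls.

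A reader might infer more, and the documents do not support it:

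- **That every patient-control contrast shrinks.** This would need ineligible controls to respond like the patients they are compared with. Section 1 reports no elevated anxiety-potentiated startle in GAD and calls the findings in MDD contradictory, so a contrast could narrow or widen.
- **That a loss of power can be stated.** Any such figure would rest on an assumed share of ineligible controls and an assumed direction.
- **That old control data are set against current patient data.** The schedule in section 8 lists a SCID for patients at the first session. But section 4.b has mood patients arriving already cleared under 01-M-0254, with no limit on how old that clearance may be.
- **That the questionnaire regressions are compromised.** Section 10 specifies them only for sub-study 3, which section 4.a reports as stopped.

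**What to change.** 1. In section 3.c, state that the 6-month look-back runs back from the date of screening for this study (01-M-0254/03-M-0093).
2. In section 4.c, require that for any reused SCID, whatever its age, the clinician at the existing screening visit completes and documents an interval update of the current-disorder and alcohol/substance sections. A trigger at 6 months would not be enough: a 3-month-old SCID already leaves half the look-back uncovered and says nothing about status since then.
3. Re-administer trait STAI, and any symptom questionnaire used in analysis, instead of importing the scores.

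The cost is a short added interview and some questionnaire time, for reused volunteers only, at a visit that already takes place. No new staff are needed.

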- **Sub-study 1: fear-potentiated startle and anxiety-potentiated startle:** Sub-study 1 will test 110 patients and 44 healthy controls (See 10. STATISTICAL ANALYSIS). This experiment examines fear and anxiety responses during anticipation of predictable and unpredictable aversive events (shocks or airpuffs). There are three different conditions, neutral (N), unpredictable aversive events (U), and predictable aversive events (P). Each of these conditions will be signaled by a written text displayed on a computer monitor (e.g., shock only when blue square present). In each condition, an additional cue (e.g., blue square) will be presented. The cues will be different for P, N, and U. They will be meaningless in the U and N conditions. However, in the P condition they will signal a possible shock/airpuff. The cues will be presented for 8 sec. The N, P, and U conditions will last approximately 2 minutes each. The cues will be presented twice per condition. These conditions will be presented in two blocks with the following predetermined orders: 1) P-N-U-N-U-N-P (FPS1) and 2) U-N-P-N-P-N-U (FPS2). The two blocks will be counterbalanced across subjects. In the P condition, 25-35% of the cues will be reinforced with an aversive event. Variation in fear and anxiety will be evaluated with the startle reflex evoked by loud sounds (see below).
 - **Saliva:** Up to 10 saliva samples per subject may be obtained to measure levels of cortisol and DHEA-S. Samples will be collected just after screening during study visit 1, after baseline heart-rate assessments during study visits 1 and 2, before and after the verbal-threat task of study visit 1, before and after the aversive-conditioning procedure and before and after the retention of aversive-conditioning procedure of study visit 2. Although cortisol samples would ideally be collected at the same time of day for all subjects, doing so would significantly slow data collection. Because cortisol analyses are of secondary importance to the current protocol and because time of collection can be statistically controlled during analyses, saliva will be collected during morning or afternoon visits, the time at which the samples are collected will be documented, and the variance associated with time of day will be covaried out of cortisol analyses. Of

note, each participant will be scheduled consistently in morning or afternoon time-slots to reduce the within-subject variability in the time saliva samples are collected.

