10. STASTISTICAL ANALYSIS

The overall target N for the protocol is 663 healthy controls and 608 patients. Participants who drop out will be replaced. Participants may participate in more than one sub-study.

- Sub-study 1
 - **Analysis of data/study outcomes:** Startle amplitude during the verbal threat procedure will be averaged over cue and no cue (ITI) periods within conditions. There will be separate analyses for anxiety disorders and mood disorders. The data will be submitted to a Group (GAD, SAD, panic disorder, control or MDD, bipolar, control) x Condition (P, N, U) x Cue (cue, ITI) ANOVA. If this interaction is significant, within-group simple-effects comparing startle amplitudes during the ITI of predictable versus unpredictable conditions will be compared for all groups separately. Larger startle magnitudes in the unpredictable versus predictable condition suggest heightened sensitivity to unpredictability. Between group contrasts will also be computed to compare difference scores (i.e., differences between startle magnitudes during unpredictable and predictable conditions) across groups. In our pilot and published studies, we obtained the lowest effect size ($f=0.30$) for contextual fear (anxiety-potentiated startle).

- **Power analysis:** We set power at .80 and experiment-wise, two-tailed alpha at 0.05. Based on these parameters, we will need 18 subjects per group. Assuming a 15 % unusable data rate due to lack of startle response or equipment failure, approximately 22 subjects per group will be recruited for a total of 110 patients and 44 healthy controls.
- Sub-study 2
 - **Analysis of data/study outcomes:** Startle amplitude will be averaged over conditions (safe, threat) and WM load (View, 1, 2, 3). There will be separate analyses for anxiety disorders and mood disorders. The data will be submitted to a Group (GAD, SAD, panic, controls or MDD, bipolar, controls) x condition (safe, threat) x WM load (1-back, 2-back, 3-back).

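### Sub-study 1 counterbalances block order, but the planned ANOVA and U-minus-P contrasts carry no order term, and the plan does not say that order is balanced within each diagnostic group

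*Combined protocol and SAP*

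**What the plan says.** Section 4.d (Sub-study 1) fixes two run sequences, "1) P-N-U-N-U-N-P (FPS1) and 2) U-N-P-N-P-N-U (FPS2"), and adds: "The two blocks will be counterbalanced across subjects". It gives no further allocation rule. It does not say whether the two orders are to be equal within each diagnosis and within controls, or only over the whole sample.

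Section 10 (Sub-study 1) collapses the blocks: "Startle amplitude during the verbal threat procedure will be averaged over cue and no cue (ITI) periods within conditions". The model is Group "x Condition (P, N, U) x Cue (cue, ITI) ANOVA", with two sets of groups: "There will be separate analyses for anxiety disorders and mood disorders". The follow-up tests are within-group comparisons of ITI startle in U and P, and then: "Between group contrasts will also be computed to compare difference scores". Neither the ANOVA nor the contrasts name order. Section 10 also says that dropouts are replaced, without saying which order a replacement receives.

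For salivary cortisol, which section 4.d treats as secondary, time of day is to be covaried out. No comparable adjustment is stated for startle, which section 9 lists as a primary outcome.

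**The concern.** Block order is a factor that the investigators assign, and it bears directly on the contrast that answers Objective 1. P opens the session in one order and U opens it in the other. If startle falls steeply over the first runs, whichever condition comes first looks larger. U-minus-P is then pushed down in subjects who start with FPS1 and up in those who start with FPS2.

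With no order term, that difference between subjects stays in the error. If diagnostic groups also differ in their mix of orders, part of a group difference in U-minus-P could come from order and not diagnosis. With 18 evaluable subjects per group, uneven splits are not rare unless the assignment prevents them.

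**Working it through.** **The plan's own figure.** 18/(1 − 0.15) = 21.2, rounded up to 22 per group; 5 × 22 = 110 patients and 2 × 22 = 44 controls. The inflation reproduces. The basis for 18 is a separate question and is not used here.

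**Step 1: positions.** I read section 4.d as giving every subject both blocks, 14 runs in all. With FPS1 first:
- P at 1, 7, 10, 12: mean 30/4 = 7.5
- U at 3, 5, 8, 14: mean 30/4 = 7.5
- N at 2, 4, 6, 9, 11, 13: mean 45/6 = 7.5

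With FPS2 first, P and U swap positions and the means are unchanged. A linear trend therefore drops out of U-minus-P in every subject, in either order.

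**Step 2: non-linear decline.** The documents give no decay rate, so take an assumed amplitude exp(−(t − 1)/τ) at run t. For τ = 3 with FPS1 first:
- mean over P = (1 + 0.135 + 0.050 + 0.026)/4 = 0.303
- mean over U = (0.513 + 0.264 + 0.097 + 0.013)/4 = 0.222
- U − P = −0.081, and +0.081 with FPS2 first

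| τ (runs) | U − P, FPS1 first / FPS2 first | difference between orders |
|---|---|---|
| 1 | −0.212 / +0.212 | 0.42 |
| 2 | −0.133 / +0.133 | 0.27 |
| 3 | −0.081 / +0.081 | 0.16 |
| 5 | −0.034 / +0.034 | 0.07 |
| 7 | −0.017 / +0.017 | 0.03 |

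Units are fractions of the decaying amplitude. The effect is real for a fast early decline and nearly gone for a slow one.

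**Step 3: lost precision.** Let D be the difference in mean U − P between the two orders, in residual SDs (assumed; not in the documents). With half the subjects in each order, the unmodelled variance is D² × ½ × ½ = D²/4. The n per group that offsets it is 18 × (1 + D²/4), rounded up; dividing by 0.85 gives the number recruited.

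| D | variance factor | evaluable n | recruited n |
|---|---|---|---|
| 0.2 | 1.01 | 18.2 → 19 | 23 |
| 0.5 | 1.0625 | 19.1 → 20 | 24 |
| 0.8 | 1.16 | 20.9 → 21 | 25 |

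**Step 4: uneven splits.** If only the 154 subjects overall were balanced 77/77, the hypergeometric chance that a given group of 22 splits 14/8 or worse is 0.25, and 15/7 or worse 0.105. If order fell independently at 50:50, a two-group contrast at 18 per group would shift with SD D × √(2 × 0.25/18) = 0.167D: 0.03, 0.08 and 0.13 SD for D = 0.2, 0.5 and 0.8.

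Averaged over such splits, simulated type I error of the unadjusted two-sample test was 0.051, 0.050 and 0.050. Conditional on a marked 12/6 against 6/12 split, the shift is D × (12 − 6)/18 = D/3, and simulated type I error was 0.054, 0.069 and 0.096. With order exactly 9/9 in both groups the contrast does not shift, but the unadjusted test is conservative: 0.049, 0.043 and 0.035.

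**The case against.** The strongest reply is that the design already does most of the work. The mirror-image blocks remove linear drift within each subject, counterbalancing is itself a control for order, and only curvature remains. That stands, and it is why the effect is modest.

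A second reply is that lost precision and a shifted contrast are not two separate harms. This also stands. The variance that chance imbalance adds to the contrast, (D²/4) × (2/18), is the square of the 0.167D shift in step 4, and the enlarged standard error already covers it on average. What remains is conditional: a particular sample with a lopsided split is biased, and the unadjusted analysis cannot show it.

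A third reply is that D has no anchor in the documents. It is correct. On the step 2 model, D = 0.5 needs an early decline of about 0.5/0.42 = 1.2 residual SDs of U-minus-P at τ = 1, and about 0.5/0.16 = 3.1 at τ = 3. Values of D of 1 or more would need about twice that or more, and nothing in the documents supports them.

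A reader might infer that order is unbalanced within diagnosis. The documents do not say so: across-subject counterbalancing neither provides for nor rules out balance within each group. A reader might also infer that the planned test is invalid or that this omission leaves the sub-study underpowered. The first fails because average type I error stays near 0.05. The second fails because any shortfall at 18 per group would exist with order fitted as well.

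**Conclusion.** The omission can be seen in the text: order is assigned by design and then left out of the ANOVA and the U-minus-P contrasts, and balance within diagnosis is not stated. The main consequence is a modest loss of precision, 1% to 16% in the variance of U-minus-P for an assumed D of 0.2 to 0.8, or about 1 to 3 subjects per group. Bias arises only conditionally, when a non-linear decline coincides with an uneven split of orders between groups.

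This rests on two assumptions: the range for D, and the reading that each subject receives both blocks. If each subject received only one block, the order difference in U-minus-P would be at least twice as large (0.36 against 0.16 at τ = 3), so the protocol should say which applies. This is an efficiency and pre-specification improvement, worth making because it is nearly free.

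**What to change.** - **Assignment (section 4.d, Sub-study 1).** State that each subject receives both blocks, if that is the intent. Assign FPS1-first and FPS2-first in equal numbers within each diagnostic group and within controls (11/11 of 22 recruited), with each replacement taking the order of the subject replaced.
- **Analysis (section 10, Sub-study 1).** Include Order (FPS1 first or FPS2 first) as a between-subject factor, with Order x Condition, in the ANOVA, and adjust the between-group U-minus-P contrasts for Order.

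The cost is two sentences and a few error degrees of freedom. In a two-group contrast at 18 per group and d = 0.60, fitting Order when it has no effect changes power only from 0.417 to 0.416. A within-subject Block factor is not needed to remove this variance, and the sample size need not change. Fixing the adjustment now also prevents it from being chosen after the data are seen.
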